# 5.4 Breaking the Blind

Unblinding by request of an Investigator should occur only in the event of an emergency or AE, for which it is necessary to know the study drugs to determine an appropriate course of therapy for the participant. If the Investigator or qualified designee must identify the treatment assignment of

an individual participant, the Investigator or qualified designee should request the treatment assignment from the IRT system. The Investigator is advised not to reveal the treatment assignment to other sites or Sponsor personnel.

Prior to unblinding, and if the situation allows, the Investigator should consult with the Sponsor's Medical Monitor. If this is impractical, the Investigator must notify the Sponsor's Medical Monitor as soon as possible, without revealing the treatment assignment of the unblinded participant. The Investigator must document the participant identification and the date and time for breaking the blind and must clearly explain the reasons for breaking the blind.

Medically necessary care should not be delayed for unblinding information (ie, the Investigator should treat the participant based on the participant's signs/symptoms without waiting for the unblinding process to be completed).

For participants who are unblinded and withdrawn from the study, study staff should make every effort to complete the full panel of assessments scheduled for the Early Termination Visit and complete a Safety Follow-up Visit (Visit 5) 4 weeks after the last dose.

## 5.5 Drug Supplies

## 5.5.1 Formulation and Packaging

The study drugs consist of 10 mg obicetrapib tablets or matching placebo tablets and over-encapsulated 10 mg ezetimibe tablets or matching placebo capsules. All study drugs are manufactured in accordance with International Council for Harmonisation (ICH) current Good Manufacturing Practice.

Obicetrapib tablets are round, white film-coated tablets, with no identifying markings, containing 10 mg of obicetrapib calcium drug substance.

Placebo tablets for obicetrapib are matching round, white film-coated tablets, with no identifying markings.

Ezetimibe capsules are 10 mg ezetimibe tablets filled into capsule shells, 1 tablet per capsule. Each capsule also contains an excipient material, common to the tablets, as a filler to prevent the tablet from rattling in the capsule shell.

Placebo capsules to match the ezetimibe capsules are the identical capsule shells filled with the excipient filler material only (no tablets).

Obicetrapib and placebo tablets and ezetimibe and placebo capsules will be packaged into kits providing the 2 study drugs for each treatment group. The kits will be clearly labelled to indicate which tablets/capsules to use on each day. Each kit will provide a sufficient supply for 28 days of dosing, with enough for an extra 4 days of dosing in case the participant needs to postpone the next visit. The shelf-life will be assigned based on the stability of the individual study drugs and will not be greater than the expiry date of the input ezetimibe tablets. The kits will be stored below 25°C.

The physical, chemical, and pharmaceutical formulation properties and characteristics of the obicetrapib tablets are described in the Investigator's Brochure.

All study drugs will be labelled in accordance with all applicable local regulatory requirements.

# 5.5.2 Study Drug Preparation and Dispensing

The study drugs include obicetrapib 10 mg, ezetimibe 10 mg, and matching placebo for each. Participants will be randomized to receive combination therapy (obicetrapib 10 mg + ezetimibe 10 mg [administered as one 10 mg obicetrapib tablet and one 10 mg ezetimibe capsule]); obicetrapib monotherapy (obicetrapib 10 mg [administered as one 10 mg obicetrapib tablet and 1 placebo capsule]), or placebo (administered as 1 placebo tablet and 1 placebo capsule) on Day 1 to Day 84. Study drugs (1 tablet and 1 capsule) will be administered by the participant orally with water, once daily on Day 1 to Day 84 at approximately the same time each morning.

At Visit 2 (Day 1), participants will receive 1 kit (containing 32 obicetrapib tablets or matching placebo tablets and 32 ezetimibe capsules or matching placebo capsules totaling 64 tablets/capsules per kit) with the study drugs appropriate for the participant's treatment group. At Visit 3 (Day 28), participants will receive 2 kits as described above. Each kit will provide a sufficient supply for 28 days of dosing, with enough for an extra 4 days of dosing in case the participant needs to postpone the next visit. Participants will be instructed to take 2 units from the kit each day. The kit will be clearly labelled to indicate which tablets/capsules to use on each day. Participants will be instructed to bring all unused study drugs to the site at the next visit.

This study protocol includes contingency measures to manage disruptions due to COVID-19 control measures, including modifications to study drug dispensation specific to situations where COVID-19 is impacting study conduct. See Section 3.1.4 for details of COVID-19 contingency measures. In the absence of a COVID-19 impact, it is expected that Investigators and participants follow the protocol requirements as set forth.

## 5.5.3 Study Drug Administration

Study drugs (1 tablet and 1 capsule) will be administered by the participant orally with water, once daily on Day 1 to Day 84 at approximately the same time each morning. On days with visits scheduled, study drugs should be administered with water following all fasted blood samples. At Visits 3 and 4, participants will dose from the kit received at the previous visit (Visits 2 and 3, respectively).

If a participant forgets to take study drug on a given day, they should take the next dose as normal and should not take a double dose to make up for the forgotten dose.

## 5.5.4 Treatment Compliance

Compliance to the study drug regimen will be evaluated by counting unused tablets and capsules. Participants will be instructed to bring all unused study drugs to the site at Visits 3 and 4. During the Treatment Period, if compliance is not between 80% and 120%, inclusive, the participant will be counselled about the importance of compliance to the regimen. If the limits are exceeded at 2 consecutive visits, a decision will be made by the Investigator and Sponsor as to whether the participant should be withdrawn from the study.

# 5.5.5 Storage and Accountability

All study drugs must be stored below 25°C (77°F) in a secure area with access limited to the Investigator and authorized site personnel.

In accordance with regulatory requirements, the Investigator or designated site personnel must document the amount of study drug dispensed and/or administered to participants, the amount returned by participants, and the amount received from and returned to the Sponsor (or representative) when applicable. Study drug accountability records must be maintained throughout the course of the study. The accountability unit for this study is a tablet or capsule. Discrepancies are to be reconciled or resolved. Procedures for final disposition of unused study drug will be provided in the appropriate study manual.

#### 5.6 Prior and Concomitant Medications and/or Procedures

#### 5.6.1 Excluded Medications and/or Procedures

Participants must not receive treatment with other investigational products or devices within 30 days or 5 half-lives, whichever is longer, prior to screening.

Participants must abstain from taking any PCSK9 inhibitor within 10 weeks prior to randomization or bempedoic acid within 2 weeks prior to randomization.

#### 5.6.2 Allowed Medications and/or Procedures

Participants must be currently receiving high-intensity statin therapy (atorvastatin 40 or 80 mg or rosuvastatin 20 or 40 mg) at a stable dose for 8 weeks prior to screening and intending to remain at the same stable dose throughout the study duration.

#### 5.6.3 Documentation of Prior and Concomitant Medication Use

Medications used within 28 days prior to the Screening Visit will be recorded. Any medications administered in addition to the study drugs, whether allowed per the protocol or not, must be documented on the concomitant medication eCRF.

# 6 STUDY PROCEDURES

Study procedures will follow the Schedule of Procedures (Appendix A).

## 7 EFFICACY AND PHARMACOKINETIC ASSESSMENTS

# 7.1 Efficacy Assessments

The primary efficacy endpoint is the percent change from Day 1 to Day 84 in LDL-C for the obicetrapib 10 mg + ezetimibe 10 mg combination treatment group compared with the placebo group.

The secondary efficacy endpoints include the following, in hierarchical order:

- Percent change from Day 1 to Day 84 in LDL-C for the obicetrapib 10 mg monotherapy treatment group compared with the placebo group;
- Percent change from Day 1 to Day 84 in ApoB for the obicetrapib 10 mg + ezetimibe 10 mg combination treatment group compared with the placebo group; and
- Percent change from Day 1 to Day 84 in ApoB for the obicetrapib 10 mg monotherapy treatment group compared with the placebo group.

The exploratory efficacy endpoints include the following:

- Percent change from Day 1 to Day 84 in non-HDL-C, VLDL-C, HDL-C, TG, ApoE, Lp(a), and HDL-ApoE for the obicetrapib 10 mg + ezetimibe 10 mg combination treatment group compared with the placebo group and for the obicetrapib 10 mg monotherapy treatment group compared with the placebo group; and
- Proportion of participants at Day 84 that achieve LDL-C <2.6 mmol/L (<100 mg/dL), LDL-C <1.8 mmol/L (<70 mg/dL), and LDL-C <1.3 mmol/L (<50 mg/dL) for the obicetrapib 10 mg + ezetimibe 10 mg combination treatment group compared with the placebo group and for the obicetrapib 10 mg monotherapy treatment group compared with the placebo group.

Blood samples for the lipid profile must be obtained under fasting conditions (ie, after the participant has fasted for approximately 10 hours). For the purposes of this study, fasting will be defined as nothing by mouth except water and any essential medications. If a participant is not fasting, the Investigator should reschedule the visit as soon as possible. LDL-C level will be calculated using the Friedewald equation unless  $TG \ge 400 \text{ mg/dL}$  or LDL-C  $\le 50 \text{ mg/dL}$ ; in both cases, LDL-C level will be measured directly by preparative ultracentrifugation, also referred to as beta quantification. Additionally, LDL-C will be measured by preparative ultracentrifugation, also referred to as beta quantification, at baseline (Visit 2) and at the end of the 12-week Treatment Period (Visit 4) for all participants.

#### 7.2 Pharmacokinetic Assessments

Plasma obicetrapib concentrations, both in combination with ezetimibe and as monotherapy, will be assessed at the scheduled PK collection times as indicated in Appendix A. At visits with dosing scheduled (ie, Visits 2, 3, and 4), PK samples will be collected with fasting laboratory samples (pre-dose). At Visits 3 and 4, the time between the last dose of study drug and PK sampling will be >24 hours. The subsequent post-dose PK sample at Visit 5 should be collected at approximately the same time as the previous visits.

# 7.3 Serum Archive Sample

A serum archive sample will be obtained at visits specified in the Schedule of Procedures (Appendix A) and stored for future analysis. If the sample is analyzed, it will be for non-genetic tests.

#### 8 SAFETY ASSESSMENTS

The safety and tolerability profile of obicetrapib 10 mg, both in combination with ezetimibe 10 mg and as monotherapy, will be assessed by clinical laboratory assessments (chemistry and hematology), vital signs, physical examinations, and the incidence of AEs.

#### **8.1** Adverse Events

An AE is defined as any untoward medical occurrence in a clinical investigation participant administered a pharmaceutical product, which does not necessarily have a causal relationship with this treatment. An AE can therefore be any unfavorable and/or unintended sign (including an abnormal laboratory finding), symptom, or disease temporally associated with the use of an investigational medicinal product, whether or not related to the investigational medicinal product. All AEs, including observed or volunteered problems, complaints, or symptoms, are to be recorded on the appropriate eCRF.

AEs, which include clinical laboratory assessment variables, will be monitored and documented from the time of first dose of study treatment until completion of Visit 5. Participants should be instructed to report any AE that they experience to the Investigator, whether or not they think the event is due to study drug. Beginning at the date of the first dose of study treatment, Investigators should make an assessment for AEs at each visit and record the event on the appropriate AE eCRF.

Wherever possible, a specific disease or syndrome rather than individual associated signs and symptoms should be identified by the Investigator and recorded on the eCRF. However, if an observed or reported sign or symptom is not considered a component of a specific disease or syndrome by the Investigator, it should be recorded as a separate AE on the eCRF. Additionally, the condition that led to a medical or surgical procedure (eg, surgery, endoscopy, tooth extraction, or transfusion) should be recorded as an AE, not the procedure itself.

Any medical condition already present at the date of the first dose of study treatment should be recorded as medical history and not be reported as an AE unless the medical condition or signs or symptoms present at baseline changes in severity, frequency, or seriousness at any time during the study. In this case, it should be reported as an AE.

Clinically significant abnormal laboratory or other examination findings (eg, ECG) that are detected during the study or are present at the date of the first dose of study treatment and significantly worsen during the study should be reported as AEs, as described below. The Investigator will exercise his or her medical and scientific judgment in deciding whether an abnormal laboratory finding or other abnormal assessment is clinically significant. Clinically significant abnormal laboratory values occurring during the study will be followed until repeat tests return to normal, stabilize, or are no longer clinically significant. Abnormal test results that are determined to be an error should not be reported as an AE. Laboratory abnormalities or other abnormal clinical findings (eg, ECG abnormalities) should be reported as an AE if any of the following are applicable:

- If an intervention is required as a result of the abnormality;
- If action taken with the study drug is required as a result of the abnormality; or
- Based on the clinical judgment of the Investigator.

## 8.1.1 Adverse (Drug) Reaction

All noxious and unintended responses to a medicinal product related to any dose should be considered an adverse drug reaction. "Responses" to a medicinal product means that a causal relationship between a medicinal product and an AE is at least a reasonable possibility, ie, the relationship cannot be ruled out.

# 8.1.2 Unexpected Adverse Drug Reaction

An Unexpected Adverse Drug Reaction is defined as an adverse reaction, the nature or severity of which is not consistent with the applicable product information.

## 8.1.3 Assessment of Adverse Events by the Investigator

The Investigator will assess the severity (intensity) of each AE as mild, moderate, or severe, and will also categorize each AE as to its potential relationship to study drug using the categories of yes or no.

# Assessment of severity

Mild – An event that is easily tolerated and generally not interfering with normal daily activities.

Moderate – An event that is sufficiently discomforting to interfere with normal daily activities.

Severe – An event that is incapacitating with inability to work or perform normal daily activities.

## Causality assessment

The relationship of an AE to the administration of the study drug is to be assessed according to the following definitions:

No (unrelated, not related, unlikely to be related) – The time course between the administration of study drug and the occurrence or worsening of the AE rules out a causal relationship and another cause (concomitant drugs, therapies, complications, etc) is suspected.

Yes (possibly, probably, or definitely related) – The time course between the administration of study drug and the occurrence or worsening of the AE is consistent with a causal relationship and no other cause (concomitant drugs, therapies, complications, etc) can be identified.

The definition implies a reasonable possibility of a causal relationship between the event and the study drug. This means that there are facts (evidence) or arguments to suggest a causal relationship.

The following factors should also be considered:

• The temporal sequence from study drug administration-

The event should occur after the study drug is given. The length of time from study drug exposure to event should be evaluated in the clinical context of the event.

• Underlying, concomitant, intercurrent diseases-

Each report should be evaluated in the context of the natural history and course of the disease being treated and any other disease the participant may have.

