3.6.1 Adverse Events (AEs)

AEs will be categorized by primary system organ class and preferred term as coded using the MedDRA (version 24.1) category designations.

An overview of treatment-emergent AEs (TEAEs) will be provided including counts and percentages of participants (and event counts) with the following:

- Any TEAEs overall and by maximum severity
- Any study drug related TEAEs, overall and by maximum severity
- Any TEAEs leading to discontinuation of study drug
- Any treatment-emergent serious AEs (TESAEs)
- Any study drug related TESAEs
- Any TEAEs leading to death

The TEAEs described above will be summarized separately by System Organ Class and Preferred Term.

Listings will be presented specifically for TEAEs, TESAEs and TEAEs leading to discontinuation of study drug.

3.6.2 *Clinical Laboratory Tests*

Blood for chemistry and hematology will be obtained as indicated in Table 1 Schedule of Procedures and sent to a central laboratory for analysis. See Appendix A for a complete list of analytes. Blood samples for chemistry and hematology must be obtained under fasting conditions (i.e., after the participant has fasted for ≥ 10 hours).

Laboratory values will be summarized descriptively, including the change and percent change from baseline. In addition, shift tables will be presented to describe the change in laboratory parameter values at post-baseline visits using normal range categories (low, normal, and high).

All safety laboratory data will be presented in participants listings.

3.6.3 *Vital Signs*

Vital signs including body temperature, heart rate, and triplicate blood pressure will be measured at all scheduled visits. Triplicate blood pressure measurements will be averaged for analysis.

Values and changes from baseline will be summarized with descriptive statistics at each visit.

Separate plots will be provided for the change from baseline in systolic and diastolic blood pressure by visit.

Height and weight will be measured at the Screening Visit only. Body Mass Index (BMI) will be derived as weight/(height/100)² (kg/m²); rounded and displayed to 1 decimal place.

3.6.4 *Electrocardiograms*

A single, standard 12-lead ECG will be performed on-site at the Screening Visit and read locally.

ECG data will be summarized with descriptive statistics and presented in participant listings.

3.6.5 *Physical Examinations*

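### The Yes and No causality rules in Protocol 8.1.3 are not complements: two of the four combinations of timing and other cause have no category, and one of them conflicts with Protocol 8.1.1

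*Protocol*

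**What the plan says.** Protocol 8.1.3 asks the investigator to "categorize each AE as to its potential relationship to study drug using the categories of yes or no". There is no third or undetermined category.

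The Causality assessment text then defines the two answers by a label and a rule.

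- The label for Yes begins "Yes (possibly, probably, or definitely related". Its rule is a time course that "is consistent with a causal relationship and no other cause (concomitant drugs, therapies, complications, etc) can be identified".
- The label for No begins "No (unrelated, not related, unlikely to be related". Its rule is a time course that "rules out a causal relationship and another cause (concomitant drugs, therapies, complications, etc) is suspected".

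Below the rules, the protocol explains that a reasonable possibility is meant: "This means that there are facts (evidence) or arguments to suggest a causal relationship". It then lists factors to weigh, including concomitant drugs, but does not say which answer results when timing fits and another cause is present.

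Protocol 8.1.1 defines an adverse drug reaction by a different test. The causal relationship "is at least a reasonable possibility, ie, the relationship cannot be ruled out".

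SAP 3.6.1 tabulates "Any study drug related TEAEs, overall and by maximum severity", and does the same for study-drug-related treatment-emergent serious events. The SAP has no default for events whose relatedness is unclear, and SAP 3.1.6 imputes no missing safety data.

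**The concern.** A two-category rating works only if every event falls under one definition and no event falls under both. Here each definition joins a timing condition to a condition on other causes, and an event that fails one need not satisfy the other. The mixed case, plausible timing with a competing explanation, is a case that a causality rule has to settle.

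If investigators settle it differently, the related-event counts reflect reading habits as well as the drug. An event can also meet the protocol's own definition of a reaction in 8.1.1 and still fail the rule for Yes in 8.1.3.

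**Working it through.** No figure in the plan bears on this point, so the check is logical. Take timing as either consistent with causality or ruling it out, take another cause as either present or absent, and apply each rule as written.

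| Timing | Other cause | Yes rule | No rule | Result |
|---|---|---|---|---|
| Consistent | None | Met | Fails on both conditions | Yes |
| Consistent | Identified | Fails: another cause is identified | Fails: timing does not exclude causality | No category |
| Rules out | Suspected | Fails on timing | Met | No |
| Rules out | None suspected | Fails on timing | Fails: no other cause suspected | No category |

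Two of the four combinations have no category.

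**Second row.** The rest of the protocol points away from the Yes rule.

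- 8.1.1: the relationship has not been ruled out, so the event counts as a reaction.
- Label on Yes: it includes possibly related, which is wider than a rule requiring that no other cause be identifiable.
- Explanatory text: a reasonable possibility needs only facts or arguments suggesting causality, and the presence of another cause does not remove these.

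An investigator who follows the label or 8.1.1 marks Yes. One who follows the explicit clause on other causes cannot.

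**Fourth row.** The label on No and the 8.1.1 test both suggest No, but the No rule as written is not met. This gap is less consequential, because nothing in the text pulls toward Yes.

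**Suspected but not identified.** The two rules use different words for the other cause. If timing is consistent and another cause is only suspected, an investigator can still read the Yes rule as met. The gap in the second row is certain only once another cause is identified.

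**Effect on the tabulated rate.** In one arm, let r be the proportion of participants with at least one clear Yes event. Let a be the further proportion whose only candidate events fall in the second row. If fourth-row events are marked No, the reported related proportion lies between r (all second-row events marked No or left blank) and r + a (all marked Yes). The documents give neither r nor a.

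**The case against.** The strongest reply is that the text steers mixed cases sufficiently. The label on Yes, the explanatory text and 8.1.1 all favour Yes, and Protocol 11.4 has the eCRF completion procedures reviewed with sites before enrolment. It stands that mixed events can be marked related. But those texts contradict the Yes rule without amending it, and an investigator who applies the rule as written is not in error. The completion procedures are not among the documents, so inconsistency between the roughly 20 sites is a risk inferred from the wording and has not been shown.

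The reply is right to limit the reach of the point. Four stronger readings might be inferred, and the documents do not support them.

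- **The background statin always supplies another cause.** The Yes rule fails only when another cause can be identified. Taking a statin does not make it the identified cause of every event, and Protocol 4.1 requires a stable dose for 8 weeks before screening.
- **Related events will be undercounted.** That assumes investigators default to No. The labels and 8.1.1 lean the other way.
- **Safety reporting in general is compromised.** Under Protocol 8.3, every SAE from first dose to 30 days after the last dose is reported whatever its causality. The scheduled follow-up visit falls 112 − 84 = 28 days after the planned last dose, inside that window. Relatedness decides investigator reporting only afterwards. Under 8.5 the sponsor or its designee makes SUSAR reports, and nothing there ties it to the investigator's answer alone.
- **The arms will be biased against each other.** Assessors are blinded and the same rule applies in all three arms. No differential effect is shown.

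**Conclusion.** The defect is real and narrow. The two rules in Protocol 8.1.3 leave two of four combinations without a category, and in the more important one the Yes rule conflicts with 8.1.1 and with its own label and explanation.

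It affects three things: the related-TEAE and related-TESAE counts in SAP 3.6.1, the related-only SAE reporting after the 30-day window in Protocol 8.3, and the causality input to SUSAR classification in Protocol 8.5. The counts are descriptive, since SAP 3.6 applies no inference to safety endpoints. Total AEs, in-window SAE reporting, efficacy and power are unaffected.

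The size cannot be derived. A reader might assume that some share of an arm has ambiguous events and read that share as the range of the related rate. That would set the clear-Yes proportion r to zero. The supportable statement is that the rate lies between r and r + a, with both unknown. The direction is also open. The conclusion rests on the wording of the protocol and SAP alone, and eCRF guidance outside these documents could narrow the gap in practice.

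**What to change.** Reconcile the definitions in 8.1.3 with 8.1.1 so that the two categories are exhaustive and mutually exclusive.

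- **Yes:** a causal relationship is a reasonable possibility, meaning that it cannot be ruled out, even if another cause is also possible.
- **No:** there is no reasonable possibility of a causal relationship, because timing rules it out or because another cause explains the event.

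This places the second row of the table under Yes unless the other cause leaves no reasonable possibility for study drug, and the fourth row under No. Carry the same wording into the eCRF completion guidelines. If any events were assessed under the present wording, say in the Clinical Study Report which definition applied.

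The cost is a text change in the protocol and guidelines. No visit, sample or analysis changes. The downside is that the reported related-event rate may rise slightly.
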